#### 4.2 Cilostazol Adverse Effects

For cilostazol's relationship to milrinone (PDE3 inhibitor inotrope) a theoretical concern was raised that cilostazol may increase the risk for sudden death or may worsen congestive heart failure with reduced ejection fraction as detailed below: However, in the studies that led to FDA approval in 1999, cilostazol was determined to have a good safety profile. In a randomized study of 1,439 patients that included recovered ejection fraction heart failure patients, the 36 months cumulative mortality rates were 6.8% in the placebo group and 5.6% in the cilostazol group, a non-significant difference. Despite an absence of adverse outcomes, a precautionary safety warning for patients with reduced ejection fraction congestive heart failure was included in the drug label. Nevertheless,

MEDICAL PROTOCOL (HRP-590)

PROTOCOL TITLE: **Cilostazol for HFpEF**

VERSION DATE: 05.16.2020

cilostazol is sometime used as a modestly effective inotrope (agent that increases cardiac contractility) in end-stage heart failure with a reduced ejection fraction.

**The most common cilostazol adverse effect is a headache (+20% over placebo), abdominal symptoms and diarrhea (+12% over placebo) and palpitations (+9% over placebo).**

The aforementioned milrinone, which is more potent than cilostazol, was recently reported to improve HFpEF. In the US, milrinone is only approved as an intravenous agent (9). Similarly, levosimendan was recently reported to provide hemodynamic and symptomatic benefits (10).

The package insert includes the risk of left ventricular outflow tract obstruction, any type of heart failure, bleeding dyscrasias, blood dyscrasias and drug interactions

Source: [https://www.accessdata.fda.gov/drugsatfda\\_docs/label/2007/020863s021lbl.pdf](https://www.accessdata.fda.gov/drugsatfda_docs/label/2007/020863s021lbl.pdf)

**Detail the FDA exemption:**

After reviewing the information contained in your submission, we have concluded that your study, "Cilostazol for HFpEF," meets all of the requirements for exemption from the investigational new drug (IND) regulations and, therefore, an IND is not required to conduct your investigation.

The IND regulations [21 CFR 312.2(b)] state that the clinical investigation of a drug product, including a biological product, that is lawfully marketed in the United States, is exempt from the requirements for an IND if all of the following apply:

- (1) The investigation is not intended to be reported to FDA as a well-controlled study in support of a new indication for use, nor intended to be used to support any other significant change in the labeling for the drug.
- (2) The investigation is not intended to support a significant change in the advertising for a prescription drug product.
- (3) The investigation does not involve a change in route of administration, dosage level, or patient population, or other factor that significantly increases the risks (or decreases the acceptability of risks) associated with use of the drug product.
- (4) The investigation is conducted in compliance with the requirements for institutional review (21 CFR 56) and informed consent (21 CFR 50).
- (5) The investigation is conducted in compliance with the requirements of 21 CFR 312.7, i.e., the drug may not be represented as safe or effective, nor may it be commercially distributed, for the purposes for which it is under investigation.

4.3 Drug storage/ handling and administration:

Cilostazol and placebos will be provided by the Fairview IDS pharmacy and preloaded into the 1 month pill box and given or shipped to the patient after consent is obtained.

The pill box has 31 removable medication vials for each day of the month to simplify the administration schedule and increase adherence. The study always starts at the first day of a month.

4.4 Biosafety: N/A

4.5 Stem Cells: N/A

4.6 Fetal Tissue: N/A

## 5.0 Procedures Involved

5.1 Study Design: prospective single blind placebo controlled n=1 study with 2 cross-overs

5.2 Study Procedures:

- NTproBNP on cilostazol and on placebo (see flow diagram) day 5 to 7 (5mL's) and day 25 to 28 (5 mL's) at any Fairview Lab site.
- Kansas City Heart Failure Questionnaire (KCCQ-12) will be administered by PI phone call day 7, 14, 21 and 28
- Baseline patient characteristics collected from Fairview EPIC

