## **1.0 Objectives**

### *1.1 Purpose:*

Determine if cilostazol improves symptoms and NTproBNP levels (heart failure blood marker) in heart failure with preserved ejection fraction (HFpEF) – a prevalent syndrome without evidence-based treatment.

This will be assessed in a prospective 1-month single blinded study with 2 cross-overs (n-of-1 study design with placebo and cilostazol)

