### *2.2 Preliminary Data:*

Cilostazol is approved for the use in peripheral artery disease and has been used in patients with diastolic dysfunction-induced atrial fibrillation and HFpEF. This results in a symptomatic relief and significant reductions in the heart failure blood marker BNP (7,8). In our own clinical experience, cilostazol reduces HFpEF symptoms and lowers NTproBNP by about 25% to suggest a clinical benefit that is in line with the cilostazol-induced changes in BNP in patients with atrial fibrillation (7,8). No adverse effects were noted in our own HFpEF patients that chronically take cilostazol.

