## 4.0 Study Intervention(s)

### 4.1 Description:

We propose a n-of-1 study design using the standard dose cilostazol formulation of 100mg twice a day approved in peripheral vascular disease. The patients will be blinded and serve as their own controls with two crossovers (cilostazol – placebo – cilostazol - placebo). This exploratory study is neither designed nor powered to seek a change in

[figure not shown]

the drug approval and thereby does not require an FDA investigational new drug (IND) application (see section 4.1). The study aims to minimize in-person visits during the ongoing COVID-19 pandemic.

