#### 15.4 Data Integrity:

The de-identified data will be available to all key personnel to yield a fully transparent data analysis.

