## **18.0 Provisions to Monitor the Data to Ensure the Safety of Participants**

*18.1* Data Integrity Monitoring. Describe the following:

- The PI will personally oversee the progress of the study and to ensure that it is conducted, recorded, and reported in accordance with the protocol, standard operating procedures, and applicable regulatory requirements. Maintenance of, and the assurance of, data accuracy and consistency over its entire life-cycle will be monitored by the principle investigator and [name]. NTproBNP and heart failure scores data integrity will be assessed and verified by both investigators.
- CTSI monitoring service will be utilized to provide regular monitoring visits every 6 month or if there is any concern that data integrity is compromised to assure that the study is conducted, recorded, and reported in compliance with Good Clinical Practice. Monitoring is provided at no cost to PIs.

*18.2* Data Safety Monitoring.

There is no formal DSMB. AEs and UOPs will be reported to the clinical director of heart failure [name] MD. If she recommends a change in protocol this will be directly communicated to the IRB and enrollment will be halted until the changes are approved.

The data will be continuously monitored by the PI and shared in a de-identified file amongst key personnel.

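### The principal investigator gives the patient-reported primary outcome at all four calls in a single-blind study, and no available text withholds the treatment sequence from that caller

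*Combined protocol and SAP*

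**What the plan says.** Section 1.1 describes the study thus: "This will be assessed in a prospective 1-month single blinded study with 2 cross-overs". Section 5.1 repeats the level of blinding: "prospective single blind placebo controlled n=1 study with 2 cross-overs". Section 4.1 says who is blinded and prints one order: "The patients will be blinded and serve as their own controls with two crossovers (cilostazol – placebo – cilostazol - placebo". No other role is named as blinded.

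The primary outcome in section 1.2 is the heart failure questionnaire. Section 5.2 assigns it to the PI: "Kansas City Heart Failure Questionnaire (KCCQ-12) will be administered by PI phone call day 7, 14, 21 and 28". Section 15.1 compares each patient's average cilostazol score with the average placebo score by paired t-test. Section 15.3 enters all four weekly scores in a mixed model, with a binary variable for whether the patient started on placebo or cilostazol, and adds paired Wilcoxon comparisons.

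On who could know the period:
- Section 4.3 has the IDS pharmacy preload the pill boxes. It does not say that the sequence is kept from the PI.
- The study-flow part of section 4.1 gives the two pills different appearances.
- Section 18.2 says "The data will be continuously monitored by the PI and shared in a de-identified file amongst key personnel".

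**The concern.** The KCCQ-12 is the patient's own account of symptoms, here spoken to an interviewer. If that interviewer knows which treatment the patient took that week, tone, prompting, clarification or the coding of a spoken answer can differ between cilostazol and placebo weeks. Section 2.2 records that the investigators' clinical experience of the drug is favourable, so an expectation exists in the team. Under section 11.2 some participants come from the PI's or co-investigators' own patients, who may answer their treating physician differently from a neutral caller.

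Such a shift would fall on the primary contrast itself. It could also reach individual patients, because section 7.1 returns a personal verdict of benefit or no benefit and allows a conversation with the treating provider about prescribing.

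**Working it through.** **1. Is the caller masked?**
- Single blind (1.1, 5.1), with patients as the only blinded party (4.1), leaves the PI outside the blind on a natural reading.
- Pharmacy filling of the boxes (4.3) would allow concealment but is not described as concealment.
- If the order printed in 4.1 applies to every patient, the call date alone reveals the period: days 7 and 21 follow cilostazol weeks, days 14 and 28 placebo weeks.
- The binary start variable in 15.3 implies that the starting treatment varies. In that case the date alone reveals nothing, and exposure depends on whether the PI is told the sequence, which is not stated.

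**2. Can the analysis remove a shift?** Let τ be the true effect and δ a net interviewer shift in favour of cilostazol. The patient difference is D = mean(cilostazol scores) − mean(placebo scores) = τ + δ + error. The paired t-test estimates τ + δ. In the mixed model the treatment coefficient is also τ + δ, because δ follows treatment exactly. The Wilcoxon test works on differences moved by the same δ. A larger sample makes τ + δ more precise but does not isolate τ.

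**3. The plan's own figure.** Section 15.2 gives a mean of 71, SD 19, a 25% relative difference, 80% power, a two-sided test and n = 18. The level is not stated; 5% is assumed.
- Planned difference: 0.25 × 71 = 17.75 points.
- 2 × [19 × (1.960 + 0.842) / 17.75]² = 17.99, so 18.

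The 18 reproduces as a per-group number from a two-independent-means formula, or from a paired formula with zero within-patient correlation. The present point does not depend on which was meant.

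**4. Illustration of size.** The documents give no δ and no SD of D, so both are assumed.
- With two scores averaged per treatment, a common SD of 19 and equal correlation ρ among the four scores, SD(D) = 19 × √(1 − ρ). Taking ρ = 0 gives 19; ρ = 0.72 gives 10.05, about 10.
- With τ = 0, the rejection rate is that of a noncentral t with n − 1 degrees of freedom and noncentrality δ√n / SD(D). For example, n = 18, δ = 3 and SD 19 give 3 × 4.243 / 19 = 0.670 and a rate of 0.097.

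| Assumed shift (points) | Share of 17.75 | n = 18, SD 19 | n = 18, SD 10 |
|---|---|---|---|
| 0 | 0% | 5% | 5% |
| 1 | 6% | 5.5% | 7% |
| 2 | 11% | 7% | 13% |
| 3 | 17% | 10% | 22% |
| 5 | 28% | 18% | 52% |

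If all 25 participants complete, a 3-point shift gives 12% (SD 19) or 30% (SD 10). The extra patients raise the error rate.

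**The case against.** Single blinding is a declared choice in a small study that section 4.1 calls exploratory. The instrument is standardised, which narrows what an interviewer can influence. NTproBNP is a laboratory value and gives a less exposed cross-check. Section 18.1 adds verification of the scores by two investigators and external monitoring visits. The pandemic aim, "The study aims to minimize in-person visits during the ongoing COVID-19 pandemic", explains the use of the telephone.

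Much of this stands and limits the weight of the point. It does not answer it. Fewer visits explain the phone but not why the PI makes the calls. Verification and monitoring are not masking. NTproBNP cannot correct a KCCQ estimate.

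Several stronger readings are tempting, and the documents do not support them:
- *That the PI is known to be unblinded at each call.* No text says so. The flow diagram and the consent pages are not available. Section 1.2 places the sample questionnaire with the consent document, so administration instructions may exist there.
- *That the printed order reveals the period at every call.* This is true only if that order applies to everyone, which 15.3 contradicts.
- *That section 15.4 opens treatment-labelled data during the calls.* It says "The de-identified data will be available to all key personnel to yield a fully transparent data analysis", which concerns analysis and gives no timing or labelling.
- *That the PI personally holds the expectation in section 2.2.* It is written as a shared impression.

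**Conclusion.** The point holds as a moderate design weakness. One person collects all the primary data, that person is not among those named as blinded, and nothing available withholds the sequence from them. That the PI knows the period is an inference, and confidence in the point is medium for that reason.

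The direction and size of any bias cannot be derived. Under the assumptions above, the false-positive rate with 18 completers runs from 5.5% to 52% across shifts of 1 to 5 points. A reader might infer that interviewer bias alone could produce the planned 17.75-point effect. The figures do not show that: even 5 points is 28% of it. What such a shift could do is make no effect, or a small one, look significant.

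**What to change.** 1. In section 4.3, state that the IDS pharmacy holds each patient's sequence and does not disclose it to whoever gives the KCCQ-12, with a code-break available for safety.
2. In section 5.2, have the KCCQ-12 given by an existing study coordinator who does not know the sequence and does not handle opened pill boxes. Ask the questionnaire before any question about pills or side effects.
3. In section 18.2, state that the caller sees no treatment-labelled data until that patient's day-28 call is recorded.

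**Precondition, a separate point.** The one order in section 4.1 and the binary start variable in 15.3 must be reconciled. If a single order is used for all, a new caller is masked only if also kept unaware of that order. Otherwise the limitation should be stated wherever the KCCQ result is reported.

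**Cost.** About 4 × 25 = 100 coordinator calls and a code-break procedure, using the pharmacy (4.3) and coordinators (25.1) already named, with no added visits or blood draws. Some unmasking will remain: a patient may describe a pill (4.1) or a side effect (section 13.1 gives headache 20 percentage points above placebo), and with alternating weeks one revealed week reveals the rest. The PI also loses a scheduled phone contact, so any safety concern raised on a call must be passed to the PI.

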## 3.0 Study Endpoints/Events/Outcomes

Endpoint/Event/Outcomes:

1. standardized heart failure questionnaire
2. NTproBNP

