#### **Cilostazol 100mg BID (white) versus Placebo BID (colored or different shape – to confirm adherence)**

The cilostazol and placebo pills are in a preloaded pill-organizer box (see below).

- study start at first day of the month (to facilitate adherence)
- two in person study visits on **day 5-7** and **day 25-28** for blood draw **and vital signs**
- four scheduled phone calls (days: **7, 14, 21 and 28**) : heart failure questionnaires

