5.4 Use of radiation: N/A

5.5 Use of Center for Magnetic Resonance Research: N/A

## 6.0 Data and Specimen Banking

6.1 Storage and Access: The primary data collected and stored a password protected UMN PCs as outlined later. In addition the data file will be encrypted and password protected. All computer equipment is in a locked office of the PI at the UMN. Data exported for analysis will only be shared as a de-identified file. The primary identifying data file will be deleted after publication.

6.2 Data:

baseline clinical patient characteristics e.g. age, gender, medications.

- 6.3 Release/Sharing: No directly identifying PHI will be released outside the University of Minnesota.

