## **7.0 Sharing of Results with Participants**

- 7.1 Patient will be informed of their personal results: benefit – no benefit.  
If requested by the participant the treating provider will be contacted to discuss the potential benefits of a cilostazol prescription.
- 7.2 Sharing of genetic testing: N/A

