## **13.0 Risks to Participants**

*13.1* Foreseeable Risks:

Headaches 34% (+20% over placebo)

Palpitations 10% (+9% over placebo)

Diarrhea 19% (+12% over placebo)

Additional Risks:

left ventricular outflow tract obstruction, any type of heart failure, bleeding

dyscrasias, blood dyscrasias and drug interactions.

*13.2* Reproduction Risks:

minimal, HFpEF is a disease outside the typical reproductive ages

*13.3* Risks to Others:

N/A

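### No scheduled contact includes an adverse-event question, and no summary by treatment is planned, so tolerability cannot be compared systematically between cilostazol and placebo weeks

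*Combined protocol and SAP*

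**What the plan says.** Contacts are described in two places. Section 4.1 plans "four scheduled phone calls (days: 7, 14, 21 and 28) : heart failure questionnaires" and "two in person study visits on day 5-7 and day 25-28 for blood draw and vital signs". Section 5.2 repeats the call schedule ("Kansas City Heart Failure Questionnaire (KCCQ-12) will be administered by PI phone call day 7, 14, 21 and 28") and adds NTproBNP sampling and baseline characteristics from the electronic record.

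The endpoints in 3.0 are "1. standardized heart failure questionnaire" and NTproBNP. Section 6.2 describes the data as "baseline clinical patient characteristics e.g. age, gender, medications". Sections 15.1 and 15.3 analyse the KCCQ and NTproBNP only.

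Side effects appear elsewhere. Section 13.1 opens its list with "Headaches 34% (+20% over placebo") and adds diarrhea at 19% (12 points over placebo) and palpitations at 10% (9 points over placebo). Section 4.2 gives the same three excesses. Under 18.2, "AEs and UOPs will be reported to the clinical director of heart failure". Section 12.1 allows withdrawal for unexpected events, with a report to the IRB, and 12.3 foresees AE data in a publication. Section 9.2 makes a general promise to monitor participants closely.

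**The concern.** The plan expects side effects and intends to report them, but it states no way of finding them out equally on both treatments. Whether a headache is recorded would depend on the patient raising it, or on the PI happening to ask, during a call scheduled for another purpose. Sections 4.1 and 5.1 blind only the patient. A caller who may know the treatment could ask more in one week than in another, and the plan has no fixed question to prevent that.

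Three things are at stake.

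- The design puts every patient on both treatments, with a call at the end of each week. A within-patient tolerability summary is therefore available without any new contact, and the plan does not take it.
- Section 7.1 says "Patient will be informed of their personal results", as benefit or no benefit, and the treating provider may be contacted about a prescription if the participant asks. No tolerability data would have been gathered in a uniform way to set beside that result.
- Section 15.2 enrols 25 to secure 18 completers, and 12.2 stops data collection at withdrawal. No instruction asks for the reason for stopping, so the report could not say reliably how much of the loss was intolerance.

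**Working it through.** **Step 1. Look for an AE item in each place where one could stand.**

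| Section | What it provides | AE question, form or summary |
|---|---|---|
| 4.1, 5.2 (calls) | Heart failure questionnaire, days 7, 14, 21, 28 | None |
| 4.1, 5.2 (visits) | Blood draw and vital signs, days 5–7 and 25–28 | None |
| 3.0 | Questionnaire, NTproBNP | None |
| 6.2 | Baseline characteristics | None |
| 15.1, 15.3 | KCCQ and NTproBNP analyses | None |
| 12.1, 12.3, 18.2 | What follows once an event is known | No means of learning of it |
| 9.2 | General monitoring promise | No procedure named |

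The last two rows deal with handling, not ascertainment. The withdrawal rule in 12.1 also concerns unexpected events, whereas those in 13.1 are forecast.

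**Step 2. Placebo rates implied by 13.1** (cilostazol rate minus stated excess).

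- Headache: 34% − 20% = 14%
- Diarrhea: 19% − 12% = 7%
- Palpitations: 10% − 9% = 1%

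**Step 3. Expected patients with each event = n × rate**, for n = 18 (planned completers, 15.2) and n = 25 (enrolled, 10.1 and 15.2). The 13.1 rates carry no time frame. Treating them as each patient's risk per treatment in this study is an assumption.

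| Event | n = 18, cilostazol vs placebo | n = 25, cilostazol vs placebo |
|---|---|---|
| Headache | 6.1 vs 2.5 | 8.5 vs 3.5 |
| Diarrhea | 3.4 vs 1.3 | 4.8 vs 1.8 |
| Palpitations | 1.8 vs 0.2 | 2.5 vs 0.25 |

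For example, 18 × 0.34 = 6.12 and 18 × 0.14 = 2.52.

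**Step 4. What a paired test could do with such data.** Let p₁ and p₀ be the two risks and ρ the within-patient correlation, assumed to lie between 0 and 0.3. Then

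P(event on both) = p₁p₀ + ρ√[p₁(1−p₁)p₀(1−p₀)].

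For headache with ρ = 0 this is 0.34 × 0.14 = 0.0476. The discordant probabilities are 0.34 − 0.0476 = 0.2924 (cilostazol only) and 0.14 − 0.0476 = 0.0924 (placebo only), together 0.3848. That is about 25 × 0.3848 = 9.6 discordant patients at n = 25. Exact two-sided McNemar power at the 5% level is:

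- Headache: 15% at n = 18; 25% to 31% at n = 25
- Diarrhea: 3% to 4% at n = 18; 9% to 10% at n = 25
- Palpitations: below 3% at either size

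A hypothesis test would therefore add almost nothing. The useful output is a descriptive table with intervals.

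**The case against.** The strongest reply is that safety is not ignored. Section 18.2 has the PI monitor the data continuously and sends AEs to the clinical director of heart failure, 12.1 and 12.3 cover withdrawal and IRB reporting, and 9.2 promises close monitoring. The study is exploratory, IND-exempt, and uses a marketed drug at its approved dose. Its aims are symptoms and a biomarker, and the analyses of those can run without AE data. All of this stands, and it limits the point to ascertainment and summary.

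A reader might go further and infer one of the following. The documents do not support them.

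- *Side effects are never asked about and cannot be compared at all.* Sections 4.1 and 5.2 say what the contacts are for; they do not rule out other questions. Spontaneous reports can be recorded under 18.2. What is missing is a specified, uniform procedure. The study-flow figure is not visible and the KCCQ-12 items are not reproduced, although nothing in the available text suggests that either covers headache, diarrhea or palpitations.
- *A patient's stopping cannot be tied to a treatment period.* The study starts on the first of the month, pills come in day-specific vials (4.3), and calls are weekly, so a stop date maps to a treatment week. What is missing is an instruction to record the date and reason.
- *Worsening heart failure goes unmeasured.* The KCCQ-12, NTproBNP and vital signs capture it in part. The gap concerns mainly headache, diarrhea and palpitations.

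One objection bears on the remedy. Reciting a list of known cilostazol side effects on day 7 could cue patients before the KCCQ-12 on days 14, 21 and 28, and patients are the only party stated to be blinded. Asking after the KCCQ-12 protects that call, not the later ones. This favours an open question over a checklist.

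**Conclusion.** The point holds in a limited form. The plan forecasts common side effects and means to report and publish AEs, yet it specifies no AE question at any scheduled contact and no summary by treatment. Events would be gathered unsystematically, by a PI not stated to be blinded, and could not be compared systematically between cilostazol and placebo weeks.

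The information at stake is modest but not negligible: for headache, an expected difference of about 3.6 patients (6.1 − 2.5) among 18 completers or 5 (8.5 − 3.5) among 25 enrolled. These counts rest on the 13.1 rates applying to short treatment periods and would be smaller if those rates reflect longer exposure. This is an inexpensive improvement to what the trial collects; it does not call the primary analysis into question.

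**What to change.** **Section 5.2.** After the KCCQ-12 at each of the four existing calls, ask one neutrally worded open question, identical in every period, about any new or worse symptoms, any stopping of study pills and any unplanned care. Record onset date, treatment week, and any stop date with its reason.

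**Section 15.** Add a descriptive table of the number of patients with each event by treatment, with intervals and no formal test.

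**Cost.** An estimated two minutes per call, one short form and one table; no new visit. Some risk of cueing patients before later KCCQ-12 calls remains. Open wording limits it but does not remove it.

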### **Exclusion Criteria:**

<18yo

resting heart rate >100/min (assessed by pulse or ECG recorded in EPIC)

patients with LVEF <50% and advanced end-stage heart failure (NYHA 3 and 4)

symptomatic COPD on home O2

uncontrolled severe HTN as defined by BP >160/100 mmHg on two checks  $\geq$ 15 minutes apart

patients with life expectancy <6 months

end-stage liver cirrhosis

more than moderate valve disease

infiltrative myocardial disease (e.g. amyloidosis) or constrictive pericarditis or myocarditis

patients unable to participate in follow up

patients without baseline LVEF data > 2 years

pregnant patients or patients without reliable contraceptive agent (intra-uterine device, birth control implant, compliance with contraception injections or contraception pills) for the duration of study participation)

left ventricular outflow tract obstruction

MEDICAL PROTOCOL (HRP-590)

PROTOCOL TITLE: **Cilostazol for HFpEF**

VERSION DATE: 05.16.2020

bleeding dyscrasias, blood dyscrasias

Patients that take: ketoconazole, itraconazole, fluconazole, miconazole, fluvoxamine, fluoxetine, nefazodone, sertraline, erythromycin, clarithromycin or azithromycin

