## **15.0 Statistical Considerations**

*15.1* Data Analysis Plan:

Primary outcomes

**KCCQ heart failure questionnaire:** paired parametric test (t-test) of placebo average composite score and the cilostazol average composite score.

**NTproBNP:** Relative changes in NTproBNP level (placebo versus cilostazol) will be compared by paired parametric testing (t-test).

*15.2* Power Analysis:

In a recent large HFpEF clinical trial of sacubitril/valsartan the baseline KCCQ score was  $71 \pm 19$ . A sample size of 18 would provide us with 80% power to detect a 25% relative difference using a 2-sided test. We propose a sample size of 25 participants to ascertain 18 or greater completed studies. In a recently completed pacemaker study that leads to a similar increase in heart rate we found a beneficial outcome in a heart failure questionnaire in n=22 participants (see reference #4, Wahlberg et al.).

*15.3* Statistical Analysis:

Linear mixed-effect models determine the effect of cilostazol on the primary outcome, accounting for inter-patient differences and treatment assignment and sequences. For the primary endpoint, the KCCQ total score at the end of each week (week 1 to 4) is the dependent variable, while the treatment (cilostazol versus placebo) is the independent variable. Patient identifier and treatment sequence (binary variable marking the start of the treatment with placebo or cilostazol) are entered as random effects. The same approach was taken to assess the effect of cilostazol on NT-proBNP levels, after log-transforming NT-proBNP values given their skewed distribution. To determine the

treatment effect paired analyses of subsequent treatment periods will be performed (Wilcoxon test) to match weeks and the days within the treatment period.

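### Drugs that interact with cilostazol are barred at entry, but no check is planned during the dosing month; one dated question on the four existing calls would add it (minor, mainly safety)

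*Combined protocol and SAP*

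**What the plan says.** Medications appear as study data once. Section 6.2 lists "baseline clinical patient characteristics e.g. age, gender, medications", and section 5.2 gives the source: "Baseline patient characteristics collected from Fairview EPIC".

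After entry, section 4.1 describes two visits (days 5–7 and 25–28) for blood and vital signs. The calls have one stated purpose: "Kansas City Heart Failure Questionnaire (KCCQ-12) will be administered by PI phone call day 7, 14, 21 and 28".

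The exclusion list in section 8.0 covers "Patients that take: ketoconazole, itraconazole, fluconazole, miconazole, fluvoxamine, fluoxetine, nefazodone, sertraline, erythromycin, clarithromycin or azithromycin", eleven drugs in all. It is an entry criterion. Section 13.1 includes among the additional risks "dyscrasias, blood dyscrasias and drug interactions".

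Section 4.3 has the tablets "preloaded into the 1 month pill box and given or shipped to the patient after consent is obtained", so there is no second dispensing step.

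On safety oversight, section 18.2 says "AEs and UOPs will be reported to the clinical director of heart failure". Section 12.1 lets the PI withdraw a patient for unexpected adverse events or unanticipated problems. Neither section names a new interacting drug as a trigger.

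**The concern.** An exclusion made for safety should hold for as long as the patient takes the drug. Several of the barred drugs can be started by another prescriber mid-month, for example a macrolide antibiotic, fluconazole or sertraline. Such a patient would continue cilostazol 100 mg twice daily until something else brought the new drug to light. The written triggers for action are adverse events and unanticipated problems, so they may operate only after harm has begun.

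A second, weaker strand is interpretation. Patients are their own controls, and NTproBNP is drawn once on each treatment. A diuretic change that acts at only one draw cannot be told apart from the treatment effect in that patient.

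**Working it through.** The plan gives no figure on this point, so there is none to reproduce. The counts below are conditional on assumptions, which are marked.

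**1. What is planned after day 1**

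| Contact | Stated content | Medication check? |
|---|---|---|
| Calls, days 7, 14, 21, 28 (4.1, 5.2) | KCCQ-12 | None stated |
| Visits, days 5–7 and 25–28 (4.1) | Blood, vital signs | None stated |
| Dispensing (4.3) | Once, before day 1 | No later occasion |
| Safety reporting (12.1, 18.2) | Adverse events, unanticipated problems | Only if an event occurs |

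**2. Overlap with cilostazol if a barred drug is started**

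From the documents: twice-daily dosing and four periods in alternation. Section 4.1 gives cilostazol first; section 15.3 allows a placebo start, so both orders are shown. Assumed: 7-day periods ending on the call days, a start day uniform over days 1–28, and dosing stopped from the day after the call that reports the drug.

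Mean overlapping doses = 2 × mean number of cilostazol days from the start of the new drug to the earlier of its end and the pause. A start at random within a cilostazol week overlaps on average 4 days of that week, or 8 doses.

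| Case | Start in week 1 / 2 / 3 / 4 | Mean |
|---|---|---|
| Cilostazol first, continued, no question | 22 / 14 / 8 / 0 | 44/4 = 11 |
| Same, with question | 8 / 0 / 8 / 0 | 16/4 = 4 |
| Placebo first, continued, no question | 28 / 22 / 14 / 8 | 72/4 = 18 |
| Same, with question | 0 / 8 / 0 / 8 | 16/4 = 4 |
| Cilostazol first, 7-day course, no question | 8 / 6 / 8 / 0 | 22/4 = 5.5 |
| Placebo first, 7-day course, no question | 6 / 8 / 6 / 8 | 28/4 = 7 |
| Either order, 7-day course, with question | as above | 4 |

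The maximum falls from 28 doses (the whole cilostazol course) to 14 (one full week). The mean saving is 11 − 4 = 7 or 18 − 4 = 14 doses for a continued drug, and 1.5 or 3 doses for a 7-day course. These are doses of overlap, not harms.

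**3. Effect on the results**

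- *One patient, NTproBNP.* Section 2.2 expects a reduction of about 25%. With an assumed 30% fall from another drug at the placebo draw only, the ratio reads 0.75/0.70 = 1.07 instead of 0.75.
- *Group NTproBNP.* Assume 4 of 18 completers have a log change of |ln 0.70| = 0.357 in random direction, and a paired log SD of 0.3 to 0.5. The expected shift is 0. The standard error grows by √(1 + (4/18) × 0.127/SD²), which is 1.146 at SD 0.3 and 1.055 at SD 0.5: about 6% to 15%.
- *Excluding those four pairs.* The interval widens by √(18/14) × 2.160/2.110 = 1.16, or 16%, which is more than the noise removed.
- *KCCQ.* If the same 4 patients all shifted by an assumed 5 points in one direction, the mean would move 4 × 5/18 = 1.1 points. That is 6.3% of the 17.75-point difference in section 15.2 (0.25 × 71).

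**The case against.** The strongest reply is that the study is small, exploratory and one month long, and that its patients are not unobserved. Section 9.2 promises close follow-up of participants, section 5.2 has the PI make the calls, section 11.2 says the investigators clinically manage these patients, and section 18.2 has the PI monitor data continuously. A new drug may well surface in conversation or in EPIC. That stands, and it keeps the point minor. None of these provisions is a planned, dated medication check, though, and a drug from an outside prescriber could be missed. The public text also lacks the consent pages and the flow figure, so an instruction to patients about new drugs may exist there. The point is limited to the text available.

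The gain is also modest. The calls come at the end of each week, so they protect the next cilostazol week and not the current one. For a short antibiotic course the saving is a few doses. This stands too.

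Stopping cilostazol has a cost of its own. Section 4.1 makes the two tablets visibly different, so telling a patient to omit only the cilostazol tablets would reveal which they are and compromise the remaining KCCQ answers. That objection is correct and shapes the fix.

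**Conclusion.** A minor point and a cheap improvement, mainly for safety. The plan applies its interaction bar at entry and plans no check of it during dosing. The benefit of adding one is unknown but probably small: on average 7 to 14 fewer overlapping doses per patient who starts and continues a barred drug, and 1.5 to 3 for a 7-day course. These figures rest on 7-day periods and a random start day. The documents give neither the frequency of such starts nor the harm per overlapping dose.

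A reader might infer that unrecorded drug changes bias the trial's conclusions. The documents do not support that. If 4 of 18 patients all had the assumed 30% fall at the placebo draw only, a true 25% reduction would read as 1 − exp(−0.288 + (4/18) × 0.357) = 18.8%. Nothing in the plan suggests that changes would be so frequent or so one-sided. Single blinding means that unequal adjustment cannot be excluded, but it is not shown. In random directions the changes add some noise and no expected shift. The 1.1-point KCCQ movement likewise requires all four patients to move the same way.

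Nor should the point be read as saying that the trial has no safety oversight. What is missing is one specific check.

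**What to change.** In section 5.2, add one dated question to the PI calls on days 7, 14, 21 and 28: since the last call, has the patient started any drug on the exclusion list, or changed a diuretic or other heart failure drug?

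A new interacting drug goes to prompt investigator review. If dosing must stop, pause all study tablets, not cilostazol alone, and record the stop and restart dates. State that a pause is not a withdrawal, because section 12.2 ends data collection on withdrawal.

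In section 15.3, report the number of changes by treatment period descriptively. Do not add a repeat NTproBNP analysis without the affected pairs: it would select on a post-treatment event and lose more precision than it recovers.

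Cost: one data field, a little call time and possibly a few paused doses. At an assumed one minute per call, the call time is 25 × 4 = 100 minutes for the whole study, or 200 at two minutes. No visit or staff is added.
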